### **3. PARTICIPANT SELECTION**

#### **3.1 Inclusion Criteria**

- Diagnosed with a CNS or PNS tumor between ages 6 months old -18 years old and will undergo treatment with at least one of the following:
  1. Targeted BRAF inhibitor therapy to treat the tumor
  2. Targeted MEK inhibitor therapy to treat the tumor
  3. Targeted pan-RAF inhibitor therapy to treat the tumor
- Patients must enroll in this trial prior to starting targeted therapy
- Subjects may participate in other studies, including therapeutic trials.
- Ability to comply with PSCR including sun protection, gentle skin care and every other day dilute bleach baths.
- Ability to understand and/or the willingness of their parent or legally authorized representative to sign a written informed consent document.

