### **5. TREATMENT PLAN**

This study aims to enroll 8 patients who will all receive in-person and written counseling for a daily preventative skin care regimen (PSCR) including instructions for daily safe sun protection, daily gentle skin care, nail care and every other day dilute bleach baths before the initiation of anti-cancer therapy. Patients will be recruited by the neuro-oncology team.

The preventative skin care regimen (PSCR) is detailed below. Patients will not have to purchase the following materials: sunscreen, gentle cleansers, moisturizers, emollients, bleach. These materials will be given to patients as the first study visit.

Safe sun protection will include instructions for:

- Use of SPF 30+ sunscreen with physical blockers (zinc oxide and/or titanium dioxide) whenever going outside
- Sunscreen to be reapplied every two hours (more often as needed)
- Sun-protective clothing including long sleeve, pants, wide-brimmed hat and sunglasses.

Gentle skin care will include:

- Daily short, lukewarm showers and water baths
- Gentle unscented cleansers (Dove, Cetaphil, Cerave, Vanicream) during bathing
- Thick and unscented moisturizing creams (Cerave cream, Vanicream, Cetaphil Cream, Dove), and emollients (Aquaphor, Vaseline) immediately following baths or showers every day.

Nail care will include:

- Trimming nails after bathing (fingernails once a week; toenails once a month)
- Keep the fingernails trimmed with a slight curve, but the toenail straight across, to prevent hangnails from forming.
- Do not pick loose bits off the nail to avoid tearing the nailbed or the cuticle.
- Cut them off neatly with a clean, sharp pair of scissors or a nail clipper.
- Avoid biting nails and trimming cuticles

Patients will also receive in-person and written counseling for every other day, 10-15 minutes dilute bleach baths.

Bleach baths will include:

- Mixing ¼ cup over-the-counter household bleach with ½ full tub of lukewarm water.
- Soak for 10-15 minutes
- Gently pat dry
- Apply gently moisturizers or emollients immediately following bathing
- In the case that patients do not have access to a tub and will make bleach bath compresses, or if a small infant tub is used, mix 1 teaspoon of bleach with 1 every 1 gallon of water

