#### 13.2 Sample Size, Accrual Rate and Study Duration

Sample Size: 22 participants from three sites (DFCI [8], Toronto Sick Kids [7], Lurie Children's Hospital [7])

Accrual Rate: 6 participants / 1 year

Study duration: ~3 years (3 years of accrual + 12 weeks of treatment on the last patient enrolled)

This sample size is limited due to the rare nature of these cancers, but a total of 22 will be sufficient for descriptive analyses. The study team believes that accrual of more than 8 patients in a one year period at DFCI/BCH\*\*\* is not feasible.

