### **13.6 Analysis of Secondary Endpoints**

In the overall cohort, the minimum, maximum, and quartiles of the number of cutaneous reactions per patient will be calculated.

In the overall cohort: To describe the severity of cutaneous reactions, the proportion of patients at each CTCAE grade of toxicity, and for each grade of the Overall Dry Skin Score (ODS), will be calculated. For each of the following severity scales, the minimum, maximum, and quartiles of the scores will be calculated: Hand-Foot Skin Reaction and Quality of Life Score (HFS-14), Pediatric Quality of Life Inventory (PedsQL), and Children's Dermatology Life Quality Index (CDLQI).

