##### **How to score it**

The scoring of each question is:

- Very much = 3
- Quite a lot = 2
- Only a little = 1
- Not at all = 0
- Question unanswered = 0
- Question 7: 'Prevented school' (text-only questionnaire) = 3
- 
- Meaning of scores
- 0-1 = no effect on child's life
- 2-6 = small effect
- 7-12 = moderate effect
- 13-18 = very large effect
- 19-30 = extremely large effect

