**7a. If **school time**: How much did your skin trouble affect your **school work**?**

Very much  
Quite a Lot  
A Little  
Not at all

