**7b. If **holiday time**: How much has your skin problem interfered with your **holiday plans**?**

Very much  
Quite a Lot  
A Little  
Not at all

**8. How much trouble have you had with your skin with other people **calling your names, teasing, bullying, asking questions, or avoiding you**?**

Very much  
Quite a Lot  
A Little  
Not at all

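### Section 13.6 pools CDLQI scores across all ages, although up to four of the ten items may not apply to infants and toddlers and an inapplicable item can only score 0

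*Combined protocol and SAP*

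**What the plan says.** Section 3.1 admits children "Diagnosed with a CNS or PNS tumor between ages 6 months old -18 years old". That is age at diagnosis; no age at enrolment is set. Section 5 expects very young participants, because it gives a bleach-bath instruction for use "if a small infant tub is used". Section 13.2 plans "22 participants from three sites".

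The calendar in section 10 schedules the severity scores at baseline, 6 weeks and 12 weeks and makes no exception by age. Section 13.6 opens its severity paragraph with "In the overall cohort: To describe the severity of cutaneous reactions" and then says of HFS-14, PedsQL and CDLQI: "For each of the following severity scales, the minimum, maximum, and quartiles of the scores will be calculated". Sections 13.3 (stratification) and 13.7 (reporting and exclusions) are marked N/A.

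Appendix A reproduces one CDLQI form for everyone. Item 3 concerns friendships and item 6 avoided swimming or other sports. Item 7a asks, in school time, "How much did your skin trouble affect your" school work; item 7b is the holiday-time alternative. Item 8 asks about other people "calling your names, teasing, bullying, asking questions, or avoiding you". The form tells the respondent to tick every question and has no 'not applicable' choice. The scoring text gives 0 both to the lowest answer and to an unanswered question. The documents contain no CDLQI age range, infant version, proxy rule or rule for inapplicable items.

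**The concern.** For a child with no school, no sports and no friendships in the sense of the form, a carer can tick the lowest answer or leave the item blank. Both give 0, so the total records the item as showing no effect. A school-age child's total can reach 30. An infant's total may have a lower ceiling, and nothing in the reported quartiles would show it.

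The trial is single-arm and descriptive, so the level of the score is the result, and no control group carries the same bias. The CDLQI is one of the scales named in Objective 3, and the background section says more data are needed on how these reactions affect quality of life. The bias runs one way, towards mild impact, and grows with the share of very young children enrolled.

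**Working it through.** **Inputs from the documents.** Ten items scored 0 to 3. Unanswered item = 0. Bands: 0-1 none, 2-6 small, 7-12 moderate, 13-18 very large, 19-30 extremely large (Appendix A). Planned N = 8 + 7 + 7 = 22 (section 13.2).

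**Reproducing the plan's figure.** Maximum = 10 × 3 = 30, which matches the top of the printed scale.

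**Ceiling with k inapplicable items at 0.** Maximum = (10 − k) × 3. For k = 4 this is 6 × 3 = 18, so the 19-30 band cannot be reached. For k = 3 it is 7 × 3 = 21.

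**Band shift.** For each possible sum s on the remaining items, compare the band of s with the band of s × 10/(10 − k), rounded to the nearest integer. Proration is only a yardstick here. It assumes the missing items would have been answered at the child's own average level.

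| Items at 0 (k) | Maximum | Possible sums | No shift | One band | Two bands |
|---|---|---|---|---|---|
| 4 | 18 | 19 | 4 | 14 | 1 |
| 3 | 21 | 22 | 10 | 12 | 0 |
| 2 | 24 | 25 | 17 | 8 | 0 |
| 1 | 27 | 28 | 24 | 4 | 0 |

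Examples with k = 4:
- Every applicable item at level 1: 6 × 1 = 6 (small) against 10 × 1 = 10 (moderate), one band.
- Every applicable item at level 2: 6 × 2 = 12 (moderate) against 10 × 2 = 20 (extremely large). This is the single two-band case.
- Every applicable item at level 3: 18 (very large) against 30 (extremely large), one band.
- s = 7: 7 × 10/6 = 11.7, rounded to 12, still moderate. The other sums with no shift are 0, 2 and 3.

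**Effect on the planned quartiles.** The documents give neither the age mix nor an item distribution, so both are assumptions. If ages were uniform from 0.5 to 18 years, (4 − 0.5)/17.5 = 20% would be under 4 (4.4 of 22) and (5 − 0.5)/17.5 = 26% under 5 (5.7 of 22). That motivates four to six children as an illustration. Cohorts of 22 were simulated with four items set to 0 in the young children, under three models:
- A: independent items, probabilities 0.40, 0.40, 0.15, 0.05 for scores 0 to 3. Mean total 8.5 on ten items, 5.1 on six.
- B: independent items, probabilities 0.25, 0.40, 0.25, 0.10. Mean total 12.0 on ten items, 7.2 on six.
- C: each child has a severity drawn from a beta(1.2, 2.5) distribution, and items are binomial(3, severity).

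Under A and B, four to six such children lower the pooled median by 0.6 to 1.2 points and the lower quartile by 0.8 to 1.8. Under C, the median falls by about 0.2 with one child, 0.8 with four and 1.2 with six. With three items at 0 instead of four, the median shift under A and B is 0.5 to 1.0 for four to six children; with two items it is 0.3 to 0.7.

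**The case against.** The count of four is a judgement about the items, not something the documents state. Item 7b asks about holiday plans, item 6 includes swimming, and item 8 includes other people asking questions or avoiding the child. A carer of a toddler with a visible rash could answer any of these. Four is therefore the upper case. A reader might infer that infants cannot score on four items at all; the wording of the form does not support that.

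A reader might also infer that young children's scores are one or two bands too mild as a rule. The table does not support that either. With four zeros, two bands occurs at one sum in 19, and four sums do not move. With three or fewer zeros a two-band shift never occurs. Section 13.6 does not tabulate bands, which appear only in the Appendix A scoring text. That objection stands for the planned output, although Appendix A gives the bands as the meaning of the scores and a reader is likely to apply them.

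The effect on the planned output is modest. Under models A and B the sampling SD of the median at N = 22 is 0.7 to 0.8 points, similar to the shift itself. Age at questionnaire can exceed age at diagnosis, so few or no infants may be assessed. The calendar row does not say that every instrument goes to every child, and no section says who completes the CDLQI. The scale is secondary, with no test or decision resting on it.

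These points limit the size. They do not supply the missing rule: as written, the plan pools all ages and has no way to record that an item does not apply.

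**Conclusion.** The concern holds as a gap in the analysis plan. Section 13.6 pools the CDLQI over a cohort that may include infants and toddlers, and the scoring counts an item that cannot apply as no effect. The bias is downward. If four items are inapplicable, the ceiling is 18 instead of 30 and the usual error for an individual child is one band. If three are inapplicable, the ceiling is 21 and 12 of 22 sums shift one band.

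For the pooled median, a shift of about 0.2 points with one such child and 0.6 to 1.2 with four to six rests on the assumed item distributions, on the assumed number of young children, and on all four items being 0. The documents fix none of these. The individual score is affected more than the pooled summary. The amendment is worth making because it is cheap and because the level of the score is what this single-arm study reports.

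**What to change.** In section 13.6, before analysis:
- State an age range for the CDLQI total, defined by age at questionnaire, not age at diagnosis.
- Compute its minimum, maximum and quartiles only in children within that range, and give the n at each visit.
- List younger children separately on the items that apply to them, without the Appendix A band labels, and do not pool the two groups.
- State which items are treated as inapplicable below the range. The choice of cut-off and items is for the study team; what matters is that it is fixed in advance.

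The cost is SAP wording and one extra table row or listing; if item-level answers are stored, no new data are needed. The downside is that the CDLQI total rests on fewer than 22 children if any fall below the range. The younger group will probably be too small for useful quartiles, so a listing is preferable to a second summary.

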### **13.7 Reporting and Exclusions**

N/A

#### **13.7.1 Evaluation of Toxicity**

N/A

#### **13.7.2 Evaluation of the Primary Efficacy Endpoint**

N/A

## **14. PUBLICATION PLAN**

The results should be made public within 24 months of reaching the end of the study. The end of the study is the time point at which the last data items are to be reported, or after the outcome data are sufficiently mature for analysis, as defined in the section on Sample Size, Accrual Rate and Study Duration.

## APPENDIX A SEVERITY SCORING SYSTEMS

### 1. Common Terminology Criteria For Adverse Events Version 5.0

[https://ctep.cancer.gov/protocolDevelopment/electronic\\_applications/ctc.htm](https://ctep.cancer.gov/protocolDevelopment/electronic_applications/ctc.htm)

Skin and subcutaneous tissue disorders					
CTCAE Term	Grade 1	Grade 2	Grade 3	Grade 4	Grade 5
Alopecia	Hair loss of <50% of normal for that individual that is not obvious from a distance but only on close inspection; a different hair style may be required to cover the hair loss but it does not require a wig or hair piece to camouflage	Hair loss of >=50% normal for that individual that is readily apparent to others; a wig or hair piece is necessary if the patient desires to completely camouflage the hair loss; associated with psychosocial impact	-	-	-
Definition: A disorder characterized by a decrease in density of hair compared to normal for a given individual at a given age and body location.					
Navigational Note: -					
Body odor	Mild odor; physician intervention not indicated; self care interventions	Pronounced odor; psychosocial impact; patient seeks medical intervention	-	-	-
Definition: A disorder characterized by an abnormal body smell resulting from the growth of bacteria on the body.					
Navigational Note: -					
Bullous dermatitis	Asymptomatic; blisters covering <10% BSA	Blisters covering 10 - 30% BSA; painful blisters; limiting instrumental ADL	Blisters covering >30% BSA; limiting self care ADL	Blisters covering >30% BSA; associated with fluid or electrolyte abnormalities; ICU care or burn unit indicated	Death
Definition: A disorder characterized by inflammation of the skin characterized by the presence of bullae which are filled with fluid.					
Navigational Note: If infectious, consider Infections and infestations; Rash pustular or other site-specific Infections and infestations term.					
Dry skin	Covering <10% BSA and no associated erythema or pruritus	Covering 10 - 30% BSA and associated with erythema or pruritus; limiting instrumental ADL	Covering >30% BSA and associated with pruritus; limiting self care ADL	-	-
Definition: A disorder characterized by flaky and dull skin; the pores are generally fine, the texture is a papery thin texture.					
Navigational Note: -					
Eczema	Asymptomatic or mild symptoms; additional medical intervention over baseline not indicated	Moderate; topical or oral intervention indicated; additional medical intervention over baseline indicated	Severe or medically significant but not immediately life-threatening; IV intervention indicated	-	-
Definition: A disorder characterized by skin which becomes itchy, red, inflamed, crusty, thick, scaly, and/or forms blisters.					
Navigational Note: -					

Skin and subcutaneous tissue disorders					
CTCAE Term	Grade 1	Grade 2	Grade 3	Grade 4	Grade 5
Hyperhidrosis	Limited to one site (palms, soles, or axillae); self care interventions	Involving >1 site; patient seeks medical intervention; associated with psychosocial impact	Associated with electrolyte/hemodynamic imbalance	-	-
Definition: A disorder characterized by excessive sweating. Navigational Note: Synonym: Night sweats, diaphoresis					
Hyperkeratosis	Present	-	Limiting self-care ADLs	-	-
Definition: A disorder characterized by a thickening of the outer layer of the skin. Navigational Note: -					
Hypertrichosis	Increase in length, thickness or density of hair that the patient is either able to camouflage by periodic shaving or removal of hairs or is not concerned enough about the overgrowth to use any form of hair removal	Increase in length, thickness or density of hair at least on the usual exposed areas of the body (face (not limited to beard/moustache area) plus/minus arms) that requires frequent shaving or use of destructive means of hair removal to camouflage; associated with psychosocial impact	-	-	-
Definition: A disorder characterized by hair density or length beyond the accepted limits of normal in a particular body region, for a particular age or race. Navigational Note: -					
Hypohidrosis	-	Symptomatic; limiting instrumental ADL	Increase in body temperature; limiting self care ADL	Heat stroke	Death
Definition: A disorder characterized by reduced sweating. Navigational Note: -					
Lipohypertrophy	Asymptomatic and covering <10% BSA	Covering 10 - 30% BSA and associated tenderness; limiting instrumental ADL	Covering >30% BSA and associated tenderness and narcotics or NSAIDs indicated; lipohypertrophy; limiting self care ADL	-	-
Definition: A disorder characterized by hypertrophy of the subcutaneous adipose tissue at the site of multiple subcutaneous injections of insulin. Navigational Note: -					
Nail changes	Present	-	-	-	-
Definition: A disorder characterized by a change in the nails. Navigational Note: -					

Skin and subcutaneous tissue disorders					
CTCAE Term	Grade 1	Grade 2	Grade 3	Grade 4	Grade 5
Erythema multiforme	Target lesions covering <10% BSA and not associated with skin tenderness	Target lesions covering 10 - 30% BSA and associated with skin tenderness	Target lesions covering >30% BSA and associated with oral or genital erosions	Target lesions covering >30% BSA; associated with fluid or electrolyte abnormalities; ICU care or burn unit indicated	Death
Definition: A disorder characterized by target lesions (a pink-red ring around a pale center). Navigational Note: -					
Erythroderma	-	Erythema covering >90% BSA without associated symptoms; limiting instrumental ADL	Erythema covering >90% BSA with associated symptoms (e.g., pruritus or tenderness); limiting self care ADL	Erythema covering >90% BSA with associated fluid or electrolyte abnormalities; ICU care or burn unit indicated	Death
Definition: A disorder characterized by generalized inflammatory erythema and exfoliation. The inflammatory process involves > 90% of the body surface area. Navigational Note: -					
Fat atrophy	Covering <10% BSA and asymptomatic	Covering 10 - 30% BSA and associated with erythema or tenderness; limiting instrumental ADL	Covering >30% BSA; associated with erythema or tenderness; limiting self-care ADL	-	-
Definition: A disorder characterized by shrinking of adipose tissue. Navigational Note: -					
Hair color changes	Present	-	-	-	-
Definition: A disorder characterized by change in hair color or loss of normal pigmentation. Navigational Note: -					
Hair texture abnormal	Present	-	-	-	-
Definition: A disorder characterized by a change in the way the hair feels. Navigational Note: -					
Hirsutism	In women, increase in length, thickness or density of hair in a male distribution that the patient is able to camouflage by periodic shaving, bleaching, or removal of hair	In women, increase in length, thickness or density of hair in a male distribution that requires daily shaving or consistent destructive means of hair removal to camouflage; associated with psychosocial impact	-	-	-
Definition: A disorder characterized by the presence of excess hair growth in women in anatomic sites where growth is considered to be a secondary male characteristic and under androgen control (beard, moustache, chest, abdomen). Navigational Note: -					

Skin and subcutaneous tissue disorders					
CTCAE Term	Grade 1	Grade 2	Grade 3	Grade 4	Grade 5
Nail discoloration	Asymptomatic; clinical or diagnostic observations only	-	-	-	-
Definition: A disorder characterized by a change in the color of the nail plate.					
Navigational Note: -					
Nail loss	Asymptomatic separation of the nail bed from the nail plate or nail loss	Symptomatic separation of the nail bed from the nail plate or nail loss; limiting instrumental ADL	-	-	-
Definition: A disorder characterized by loss of all or a portion of the nail.					
Navigational Note: -					
Nail ridging	Asymptomatic; clinical or diagnostic observations only; intervention not indicated	-	-	-	-
Definition: A disorder characterized by vertical or horizontal ridges on the nails.					
Navigational Note: -					
Pain of skin	Mild pain	Moderate pain; limiting instrumental ADL	Severe pain; limiting self care ADL	-	-
Definition: A disorder characterized by a sensation of marked discomfort in the skin.					
Navigational Note: -					
Palmar-plantar erythrodysesthesia syndrome	Minimal skin changes or dermatitis (e.g., erythema, edema, or hyperkeratosis) without pain	Skin changes (e.g., peeling, blisters, bleeding, fissures, edema, or hyperkeratosis) with pain; limiting instrumental ADL	Severe skin changes (e.g., peeling, blisters, bleeding, fissures, edema, or hyperkeratosis) with pain; limiting self care ADL	-	-
Definition: A disorder characterized by redness, marked discomfort, swelling, and tingling in the palms of the hands or the soles of the feet. Also known as Hand-Foot Syndrome.					
Navigational Note: -					
Photosensitivity	Painless erythema and erythema covering <10% BSA	Tender erythema covering 10 - 30% BSA	Erythema covering >30% BSA and erythema with blistering; photosensitivity; oral corticosteroid therapy indicated; pain control indicated (e.g., narcotics or NSAIDs)	Life-threatening consequences; urgent intervention indicated	Death
Definition: A disorder characterized by an increase in sensitivity of the skin to light.					
Navigational Note: -					

Skin and subcutaneous tissue disorders					
CTCAE Term	Grade 1	Grade 2	Grade 3	Grade 4	Grade 5
Pruritus	Mild or localized; topical intervention indicated	Widespread and intermittent; skin changes from scratching (e.g., edema, papulation, excoriations, lichenification, oozing/crusts); oral intervention indicated; limiting instrumental ADL	Widespread and constant; limiting self care ADL or sleep; systemic corticosteroid or immunosuppressive therapy indicated	-	-
Definition: A disorder characterized by an intense itching sensation.					
Navigational Note: -					
Purpura	Combined area of lesions covering <10% BSA	Combined area of lesions covering 10 - 30% BSA; bleeding with trauma	Combined area of lesions covering >30% BSA; spontaneous bleeding	-	-
Definition: A disorder characterized by hemorrhagic areas of the skin and mucous membrane. Newer lesions appear reddish in color. Older lesions are usually a darker purple color and eventually become a brownish-yellow color.					
Navigational Note: -					
Rash acneiform	Papules and/or pustules covering <10% BSA, which may or may not be associated with symptoms of pruritus or tenderness	Papules and/or pustules covering 10 - 30% BSA, which may or may not be associated with symptoms of pruritus or tenderness; associated with psychosocial impact; limiting instrumental ADL; papules and/or pustules covering > 30% BSA with or without mild symptoms	Papules and/or pustules covering >30% BSA with moderate or severe symptoms; limiting self-care ADL; associated with local superinfection with oral antibiotics indicated	Life-threatening consequences; papules and/or pustules covering any % BSA, which may or may not be associated with symptoms of pruritus or tenderness and are associated with extensive superinfection with IV antibiotics indicated	Death
Definition: A disorder characterized by an eruption of papules and pustules, typically appearing in face, scalp, upper chest and back.					
Navigational Note: -					
Rash maculo-papular	Macules/papules covering <10% BSA with or without symptoms (e.g., pruritus, burning, tightness)	Macules/papules covering 10 - 30% BSA with or without symptoms (e.g., pruritus, burning, tightness); limiting instrumental ADL; rash covering > 30% BSA with or without mild symptoms	Macules/papules covering >30% BSA with moderate or severe symptoms; limiting self care ADL	-	-
Definition: A disorder characterized by the presence of macules (flat) and papules (elevated). Also known as morbilliform rash, it is one of the most common cutaneous adverse events, frequently affecting the upper trunk, spreading centripetally and associated with pruritis.					
Navigational Note: -					

Skin and subcutaneous tissue disorders					
CTCAE Term	Grade 1	Grade 2	Grade 3	Grade 4	Grade 5
Scalp pain	Mild pain	Moderate pain; limiting instrumental ADL	Severe pain; limiting self care ADL	-	-
Definition: A disorder characterized by a sensation of marked discomfort in the skin covering the top and the back of the head.					
Navigational Note: -					
Skin atrophy	Covering <10% BSA; associated with telangiectasias or changes in skin color	Covering 10 - 30% BSA; associated with striae or adnexal structure loss	Covering >30% BSA; associated with ulceration	-	-
Definition: A disorder characterized by the degeneration and thinning of the epidermis and dermis.					
Navigational Note: -					
Skin hyperpigmentation	Hyperpigmentation covering <10% BSA; no psychosocial impact	Hyperpigmentation covering >10% BSA; associated psychosocial impact	-	-	-
Definition: A disorder characterized by darkening of the skin due to excessive melanin deposition.					
Navigational Note: -					
Skin hypopigmentation	Hypopigmentation or depigmentation covering <10% BSA; no psychosocial impact	Hypopigmentation or depigmentation covering >10% BSA; associated psychosocial impact	-	-	-
Definition: A disorder characterized by loss of skin pigment (e.g., vitiligo).					
Navigational Note: -					
Skin induration	Mild induration, able to move skin parallel to plane (sliding) and perpendicular to skin (pinching up)	Moderate induration, able to slide skin, unable to pinch skin; limiting instrumental ADL	Severe induration; unable to slide or pinch skin; limiting joint or orifice movement (e.g., mouth, anus); limiting self care ADL	Generalized; associated with signs or symptoms of impaired breathing or feeding	Death
Definition: A disorder characterized by an area of hardness in the skin.					
Navigational Note: -					
Skin ulceration	Combined area of ulcers <1 cm; nonblanchable erythema of intact skin with associated warmth or edema	Combined area of ulcers 1 - 2 cm; partial thickness skin loss involving skin or subcutaneous fat	Combined area of ulcers >2 cm; full-thickness skin loss involving damage to or necrosis of subcutaneous tissue that may extend down to fascia	Any size ulcer with extensive destruction, tissue necrosis, or damage to muscle, bone, or supporting structures with or without full thickness skin loss	Death
Definition: A disorder characterized by a circumscribed, erosive lesion on the skin.					
Navigational Note: -					

Skin and subcutaneous tissue disorders					
CTCAE Term	Grade 1	Grade 2	Grade 3	Grade 4	Grade 5
Skin and subcutaneous tissue disorders - Other, specify	Asymptomatic or mild symptoms; clinical or diagnostic observations only; intervention not indicated	Moderate; minimal, local or noninvasive intervention indicated; limiting age-appropriate instrumental ADL	Severe or medically significant but not immediately life-threatening; hospitalization or prolongation of existing hospitalization indicated; limiting self care ADL	Life-threatening consequences; urgent intervention indicated	Death
Definition: -					
Navigational Note: -					

